University of Thessaly, School of Health Sciences

Faculty of Medicine

Department of Anesthesiology

STUDY PROTOCOL

A Prospective Observational Study on Assessment of the Soluble Urokinase Plasminogen Activator Receptor in Adult Patients Undergoing Major Non-cardiac Surgery (SPARSE): Study protocol

(SPARSE: if our hypothesis is correct, the SuPAR will help to investigate whether the preoperative suPAR level can aid in identifying patients at high risk for postoperative complications, morbidity and mortality.)

BACKGROUND

Soluble urokinase plasminogen activator receptor

The biomarker soluble urokinase plasminogen activator receptor (suPAR) is the soluble form of the cell membrane-bound protein urokinase plasminogen activator receptor (uPAR), which is expressed mainly on immune cells, endothelial cells, and smooth muscle cells. uPAR is released during inflammation or immune activation, and therefore the suPAR level reflects the extent of immune activation in the individual.¹ All human beings have a baseline level of suPAR that is individually determined and increases with age. Studies have shown that the suPAR level is

associated with morbidity and mortality in a number of acute and chronic diseases and in the general population.²⁻¹⁵ The suPAR level is elevated across diseases, and not solely associated with one specific disease. Therefore, suPAR is applicable as a prognostic marker and not as a diagnostic marker. This characteristic may be utilized for risk stratification in unselected patients.

Originally, uPAR was proven a receptor for urokinase (uPA) which splits plasminogen into active plasmin. Moreover, uPAR interacts with other proteins and plays a role in several important cell processes like migration, adhesion, angiogenesis, proliferation, and chemotaxis.¹ The suPAR protein was discovered in 1991, when it was found to be a marker of cancer progression.¹ In recent years, several studies have shown that suPAR is associated with a number of chronic diseases (including cardiovascular, hepatic, renal, and pulmonary diseases), and that the level is a predictor of a negative outcome of various infectious diseases (tuberculosis, HIV, malaria, sepsis, meningitis, pneumonia) and in critically ill patients.^{2-12, 15,17-21}

Across diseases, the suPAR level discriminates non-survivors from survivors. suPAR reflects the level of chronic inflammation, and therefore it has been studied as a potential marker of development of diseases, and studies have shown that an elevated level predicts development of chronic diseases and cancer in the general population.²⁻¹⁵ The suPAR blood level is stable with no diurnal variation and no changes following fasting, while suPAR can be measured in blood, plasma, urine, cerebrospinal fluid, ascites fluid and pleural fluid.¹ The level increases and decreases with progression and improvement of a disease, respectively, but more slowly compared to e.g. C-reactive protein (CRP). The normal suPAR plasma level is 2-3 ng/mL in healthy individuals, about 3-4 ng/mL in unselected patients in emergency departments, and about 9-10 ng/mL in critically ill patients.

suPAR in intensive care

In critically ill patients, the suPAR level is significantly increased. suPAR is an independent prognostic marker, and the change over time correlates with organ dysfunction. suPAR is elevated and has a prognostic value in patients with: SIRS (systemic inflammatory response syndrome),^{22,23} sepsis/septic shock,²⁴⁻³⁰ burn injuries,³¹ and traumatic brain injuries.³² The suPAR level reflects the body's immune response to infections, and the level increases with the severity of the infection. In patients with organ dysfunction, the suPAR value is often a two-digit value. In particular hepatic and renal dysfunction affects the suPAR level.²⁴⁻²⁶ suPAR has been studied in patients with SIRS who were acutely admitted to the emergency department (n=902). The studies showed that suPAR is a stronger marker of 2-day, 30-day, and 90-day mortality than age, CRP, IL-6, creatinine, and procalcitonin. However, for diagnostic purposes, IL-6 and CRP are superior to suPAR in predicting a positive blood culture.^{22,23} A Greek multicenter study including 1914 patients with sepsis showed that suPAR is a strong predictor of mortality, and that a suPAR level above 12 ng/mL is linked to a >80% sensitivity for mortality and a negative predictive value of 94.5%.²⁷ In addition, the prognostic value of suPAR in patients with sepsis is independent of relevant covariates like APACHE score, CRP, etc.²⁷⁻³⁰

In patients with burn injuries and inhalation trauma requiring mechanical ventilation, the plasma suPAR level and bronchoalveolar lavage fluid level correlate to IL-6 and coagulation factors. An elevated plasma suPAR level is associated with prolonged Intensive Care Unit (ICU) stay and the duration of mechanical ventilation.³¹ The suPAR level is elevated in patients with traumatic brain injury. In trauma patients who suffered a brain injury within 12 hours prior to blood sampling, the mean suPAR level is $14.9 \text{ ng/mL} \pm 6.9$ vs. $2.8 \text{ ng/mL} \pm 0.7$ in control subjects. In

these patients suPAR is associated with severity of the brain injury and with mortality.³²

suPAR in surgery

The suPAR level is elevated in patients with infections, chronic diseases, and cancer compared to healthy individuals. A high suPAR level is associated with increased mortality risk,³³ poor prognosis,³⁴⁻³⁸ postoperative pneumonia,³⁹ and prosthetic joint infection.⁴⁰ suPAR is a well-studied biomarker predicting prognosis, disease severity, and organ dysfunction and is being considered as a marker of the individual's inflammatory status. It has been demonstrated that biomarkers are able to improve triage and are effective in identifying high and low risk patients among acutely admitted patients.⁴¹ Improving the preoperative risk stratification using biomarkers may optimize the patient's clinical outcome.⁴²

Available data on use of biomarkers in addition to risk stratification are observational data, and suPAR has mainly been studied in medical and oncological patients. Gastric surgery patients and orthopedic surgery patients were included in a study conducted in the emergency department at Hillerød Hospital, Denmark. The TRIAGE study included 5992 unselected patients and confirmed the prognostic value of suPAR regarding mortality, and found it similar in both medical and surgical patients.⁴¹ In the same study, it was shown that triage based on suPAR level was superior to the current triage system in predicting 30-day mortality: AUC 0.84 (0.82-0.87) vs. 0.62 (0.58-0.66), respectively. In multivariate analyses of 30-day mortality in relation to suPAR quartiles, adjusted for sex, age, CRP, leucocytes, and triage category, HR was 1.0, 2.2, 8.3, and 26.9 in the upper quartile. A high suPAR level has

been demonstrated in both tumor tissue and in blood, and in several cancers, the suPAR level is shown to correlate with a poor prognosis.⁴³ In a few studies, suPAR has been studied as a potential biomarker in gastric surgery.

In a cohort of 518 elective colorectal cancer patients, preoperative measurement of the suPAR level was performed. In multivariate analyses adjusted for age, sex, tumor classification, and localization, suPAR was significantly associated with mortality, HR 1.74 (1.33-2.26; $p<0.0001$). In addition, the suPAR level was associated with tumor stage and localization; and in colon cancer patients the suPAR level was significantly higher compared to rectal cancer patients.³⁴ The same cohort was also followed in another study, in which the suPAR plasma level was found to be an independent prognostic marker.³⁵ To identify risk patients among elective colon cancer patients the suPAR level was studied. In patients receiving blood transfusion during surgery, the suPAR level was higher, and a significant association between the suPAR level and postoperative infections was shown. Occurrence of pneumonia was significantly associated with the suPAR level, but any significant association with other infectious complications could not be found.³⁹ In patients with gastric cancer, the suPAR level was significantly higher compared to healthy controls ($2.3 \text{ ng/mL} \pm 0.77$), and the suPAR level was significantly higher in cancer patients with metastatic disease ($7.0 \text{ ng/mL} \pm 6.1$) than in patients with no metastases ($4.8 \text{ ng/mL} \pm 4.4$). In the group of patients with a suPAR value above 5.2 ng/mL , the mortality was significantly increased.³⁶ In patients with rectal cancer and colon cancer, a similar prognostic value is found, indicating an increased mortality risk.^{37,38}

The diagnostic value of suPAR in prosthetic knee/hip joint infection has been examined in a study.⁴⁰ The study included 80 patients of which 45 experienced prosthetic joint infection defined by presence of clinical signs (swelling, redness,

tenderness, and pus inside the joint) and a positive culture. In these patients, a significantly higher median suPAR level (6.8 ng/mL) was found compared to patients without infection, who had revision surgery done. Furthermore, suPAR was positively correlated with CRP, and the study showed that suPAR was more precise in diagnosing prosthetic knee/hip joint infection than CRP.

AIM

SPARSE is a single-center observational study aiming to investigate if suPAR measured preoperatively and immediately after surgery can predict the risk of future complications and post-operative mortality in adults following major non-cardiac surgery.

METHODS

Design

This is a prospective observational study designed in accordance with the declaration of Helsinki. The study will be register at Clinical Trials.gov and has been approved by the Institutional Review Board of the University Hospital of Larisa, under the reference number 60580/11-12-2018.

Patient eligibility

Consecutive patients who are scheduled to undergo elective major non-cardiac surgery with expected duration ≥ 2 hours under general anesthesia will be screened for

inclusion. All operative approaches will be eligible for inclusion, including open, laparoscopic and robotic procedures. Patients fulfilling the following inclusion criteria will be included: age \geq 18 years, and American Society of Anesthesiologists' (ASA) physical status I to IV.

Exclusion criteria will be age <18 years, any infection within the previous 4 weeks, severe liver disease, patients on renal replacement therapy pre-operatively, patients who had previously received a transplant, patients with allergies, inflammatory or immune system disorders, and/or connective tissue disease including rheumatoid arthritis, ankylosing spondylitis, and systemic lupus erythematosus, administration of steroid, antipsychotic, or anti-inflammatory/immunomodulatory medication during the 3 months prior to surgery, administration of opioids during the past week, asthma, obesity ($BMI \geq 30 \text{ kg m}^{-2}$), mental disability or severe psychiatric disease, alcohol or other abuse, legal incapacity or limited legal capacity, and subjects within the exclusion period of another study.

Management of Anesthesia and Surgical Procedures

Endotracheal intubation and anesthetic care will be performed according to our institutional routine. Intravenous induction of general anaesthesia will include midazolam 0.15-0.35 mg/kg iv over 20-30 seconds, fentanyl 1 μ g/kg, propofol 1.5-2 mg/kg, ketamine 0.2 mg/kg (intravenous bolus), and rocuronium 0.6 mg/kg. All drugs will be prepared in labelled syringes and induction will be achieved by administration of a predetermined iv bolus dose on the basis of the patient's weight and/or age. Laryngoscopy and intubation will proceed in a standard fashion, while the position of the endotracheal tube will be confirmed by auscultation and

capnography/capnometry. The patients will then connected to an automated ventilator (Draeger Primus®; Drägerwerk AG & Co., Lübeck, Germany).

All patients will be ventilated using a lung-protective strategy with tidal volume of 7 mL/kg, positive end-expiratory pressure of 6-8 cmH₂O, plateau pressures <30 cmH₂O, and recruitment maneuvers repeated every 30 min after tracheal intubation.⁴⁴ Maintenance of general anesthesia will include desflurane 1.0 MAC with 40% oxygen and 60% air, while intraoperative dose changes will be left to the anesthesiologist in charge of the patient. Depth of anesthesia (bispectral index-BIS, Covidien, France) will be monitored, with the target ranging between 40 and 60.^{45,46} Normocapnia will be maintained by adjusting the respiratory rate as needed, while normothermia (37°C) will be maintained throughout the intraoperative period.

All patients will be operated by at least two consultant surgeons who will be supervised by a Professor of Surgery.

Sampling and laboratory measurements

Participants will undergo sampling of peripheral venous blood, immediately after arrival to the OR, and at the Post-Anesthesia Care Unit (PACU). Blood samples drawn from all patients and EDTA plasma will be stored at -80° C until later measurement. Plasma suPAR levels will be determined using the suPARnostic® quick triage lateral flow assay (ViroGates, Denmark), according to the manufacturers instructions.

Microcirculation flow analysis

In addition to routine hemodynamic data, sublingual microvascular flow will be measured using noninvasive technology. We will obtain measurements preoperatively (PRE), intraoperatively (INT), and postoperatively after arrival in the PACU (POST). At each time point, we will image the microcirculatory network of the sublingual mucosa with sidestream darkfield (SDF+) videomicroscopy which has an increased optical resolution resulting in one pixel recording an area of $0.56 \mu\text{m}^2$. This device uses the new SDF+ technology that allows the red blood cells to be visualised with greater accuracy and detail, which is essential for enhancing the capabilities of the analysis application.

We will use the sublingual space as the site of imaging because it shares the same embryologic origin as the splanchnic mucosa and can reflect derangements in splanchnic blood flow; impaired sublingual microcirculatory blood flow is associated with increased mortality and worsening organ failure in patients with sepsis.⁴⁷⁻⁵¹

Outcomes

The primary endpoint will be the presence of complications and/or admission to ICU and/or mortality within the first 60 postoperative days.

Secondary endpoints will be intraoperative complications (including desaturation [$\text{SpO}_2 <92\%$ for 3 minutes or more], need for unplanned recruitment maneuvers, hypotension [defined as systolic blood pressure $<90 \text{ mmHg}$ or mean arterial pressure $<65 \text{ mmHg}$ for 3 minutes or more or need of vasoactive drugs for correction], need for unplanned vasoactive drugs [need for vasoactive drugs not

planned before and/or continuous infusion], and/or acute new arrhythmia [atrial fibrillation, sustained ventricular tachycardia, supraventricular tachycardia, and/or cardiac arrest]), reintubation, hospital length of stay, and length of stay in ICU. Secondary endpoints will also include postoperative complications within 90 days after surgery defined as in the SURPAS studies,⁵²⁻⁵⁴ with the inclusion of atelectasis and ileus, resulting in 22 possible postoperative complications, as well as survival at hospital discharge, at 90 days, and at 1 year.

Data Collection and Monitoring

Data analysis will be based on predefined data points on a prospective data collection form. The staff will be blinded to measurements until the end of the study and all data are analyzed. Clinical monitoring throughout the study will be performed to maximize protocol adherence, while an independent Data and Safety Monitoring research staff will monitor safety, ethical, and scientific aspects of the study. Data collection will include demographics, anesthesia parameters, C-reactive protein, P-POSSUM score, ACS-NSQIP score, APACHE II, SOFA, and the Charlson Age-Comorbidity Index (Charlson score).⁵⁵ We will use a SAS macro based on ICD-10 diagnoses to calculate the Charlson score.^{56,57} Two other simpler models adding predictive value to the ASA classification will be also used; the Surgical Mortality Probability Model and a similar model proposed by Glance and Donati.^{58,59}

Data management

The goal of the clinical data management plan is to provide high-quality data by adopting standardized procedures to minimize the number of errors and missing data, and consequently, to generate an accurate database for analysis. Remote monitoring is performed to signal early aberrant patterns, issues with consistency, credibility and other anomalies. Any missing and outlier data values are individually revised and completed or corrected whenever possible.

Sample size and predefined statistical analysis plan

Patients will be consecutively included during the study period, in a convenience sample and will be stratified into low-risk or high-risk groups, according to suPAR level (suPAR_{high} above and suPAR_{low} below 5.5 ng/ml), respectively.⁶⁰ An a priori power analysis was done set to detect a difference of 0.50 on the suPAR (between suPAR_{high} and suPAR_{low} group, based on the researchers' preference. The number of patients planned for recruitment was rounded up to 100 to allow for flexibility in the study. This sample size was estimated to achieve 80 percent power to detect the suggested difference. The sample size calculation was made using G*Power 3.1.⁶¹ The association between ASA classification, suPAR level, CRP and the rate of postoperative complications will be analyzed with logistic regression and Cox regression analyses, estimating odds ratios (ORs) and hazard ratios (HRs).

Ethics and dissemination

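### suPAR tracks cancer and tumour stage by the plan's own account, and cancer of any stage is eligible, yet no analysis takes malignancy into account while survival is followed to 1 year

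*Combined protocol and SAP*

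**What the plan says.** **Who is enrolled.** Patient eligibility admits adults of ASA class I to IV having elective major non-cardiac surgery. The exclusions include "any infection within the previous 4 weeks, severe liver disease, patients on renal replacement therapy pre-operatively", and go on to transplant, immune, inflammatory and connective-tissue disease, steroid and immunomodulatory drugs, asthma and obesity. Malignancy is not on the list, and stage is not restricted.

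**What the plan says about suPAR and cancer.** Under suPAR in surgery, the Background states that suPAR is raised in cancer. In colorectal cancer it is linked to tumour stage and to death. In gastric cancer, "the suPAR level was significantly higher in cancer patients with metastatic disease" than in those without metastases. The figures are 2.3 ng/mL (SD 0.77) in healthy controls, 4.8 (SD 4.4) without metastases and 7.0 (SD 6.1) with metastases.

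**What is compared.** The statistical section splits patients at 5.5 ng/ml, which lies between the two gastric cancer means. Its one modelling sentence begins: "The association between ASA classification, suPAR level, CRP and the rate of postoperative complications will be analyzed". It goes on to name logistic and Cox regression. No covariates are named for survival.

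**What is followed.** The primary endpoint is a 60-day composite of complications, ICU admission or death. The secondary endpoints include 90-day complications, "as well as survival at hospital discharge, at 90 days, and at 1 year". A Charlson score built from ICD-10 diagnoses is collected (Data Collection and Monitoring) but has no stated role in any model.

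**The concern.** On the plan's own account, malignancy and its stage are related both to the marker and to death. If suPAR-high patients more often have cancer, and more often metastatic cancer, they will die more often within a year even if suPAR says nothing beyond the diagnosis. A crude contrast cannot tell these situations apart.

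This matters because the aim names post-operative mortality, and the Background presents suPAR as a way to improve preoperative risk stratification. For elective surgery, the diagnosis and any known metastases will usually be on record beforehand. The useful question is then whether suPAR adds to them. Without a malignancy term, a positive survival result could be read as added value that the study has not shown.

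**Working it through.** The plan gives no figure for this point to reproduce: no expected cancer share, no expected share above 5.5 ng/ml, no mortality rates. Its only design figure is 100 patients at 80% power, and the argument does not depend on the power.

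**Step 1. Share above 5.5 ng/ml, from the plan's means and SDs.** Lognormal: σ² = ln(1 + (SD/mean)²), μ = ln(mean) − σ²/2, share = 1 − Φ((ln 5.5 − μ)/σ), with ln 5.5 = 1.705.

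| Group | μ | σ | z | Share above 5.5 |
|---|---|---|---|---|
| Healthy controls, 2.3 (0.77) | 0.780 | 0.326 | 2.84 | 0.2% |
| Gastric cancer, no metastases, 4.8 (4.4) | 1.264 | 0.781 | 0.56 | 29% |
| Gastric cancer, metastases, 7.0 (6.1) | 1.663 | 0.752 | 0.05 | 48% |

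A normal shape gives 0%, 44% and 60%. Either way most non-metastatic patients (56–71%) fall below the cut-off.

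**Step 2. Patients without cancer.** The documents give no distribution for them. Healthy controls are one extreme. The Background also states: "The normal suPAR plasma level is 2-3 ng/mL in healthy individuals, about 3-4 ng/mL in unselected patients in emergency departments". I therefore also try mean 3.5 with SD 1, mean 3.5 with SD 2, and mean 4 with SD 3.6. These SDs are assumed; the last gives about the relative spread of the cancer groups. Lognormal shares above 5.5 are 4.0%, 13.2% and 21.2%.

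**Step 3. Contrast produced with no suPAR effect inside any malignancy group.** Assume a case mix (none/localised/metastatic) of 60/30/10% and 1-year mortality of 2/10/45%. With healthy-like non-cancer patients:

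- suPAR-high share: 0.6 × 0.0023 + 0.3 × 0.286 + 0.1 × 0.478 = 0.135
- deaths among suPAR-high: 0.0014 × 0.02 + 0.0858 × 0.10 + 0.0478 × 0.45 = 0.0301, so mortality is 0.0301/0.135 = 22.3%
- all deaths: 0.012 + 0.030 + 0.045 = 0.087, so suPAR-low mortality is (0.087 − 0.0301)/0.865 = 6.6%
- OR = (0.223/0.777)/(0.066/0.934) = 4.1

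**Step 4. Vary every assumed input.** Each cell gives the OR under 1-year mortality of 2/10/45%, then under a flatter 5/10/30%.

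| Case mix (%) | Non-cancer as healthy | Mean 3.5, SD 1 | Mean 3.5, SD 2 | Mean 4, SD 3.6 |
|---|---|---|---|---|
| 75/20/5 | 5.3, 2.7 | 3.8, 2.1 | 2.3, 1.5 | 1.7, 1.3 |
| 60/30/10 | 4.1, 2.4 | 3.4, 2.1 | 2.3, 1.7 | 1.8, 1.4 |
| 40/45/15 | 2.8, 2.0 | 2.5, 1.8 | 2.0, 1.6 | 1.7, 1.4 |
| 60/38/2 | 2.8, 1.8 | 2.3, 1.6 | 1.7, 1.3 | 1.3, 1.2 |

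The range is 1.2 to 5.3. In the 60/30/10 row the cancer share of the suPAR-high group is 99%, 85%, 63% and 51% from left to right; in the 75/20/5 row it falls to 34%. Letting the cohort's cancer share run from 10% to 70%, under both shapes, that share spans about 12% to 100%.

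**Step 5. Information available.** At 100 patients these mixes and rates imply about 6 to 12 deaths in a year. In the Step 3 case, the suPAR-high group holds about 0.1 patients without cancer, 9 with localised disease (about 1 death) and 5 with metastases (about 2 deaths).

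**The case against.** **The stronger reading does not stand.** A reader might infer that the exclusions remove most non-malignant causes of a raised suPAR, so that the suPAR-high group would be mainly cancer patients. The documents do not support this. The Background links suPAR to cardiovascular, hepatic, renal and pulmonary disease. Cardiovascular disease, lung disease other than asthma, renal disease short of replacement therapy and non-severe liver disease all remain eligible, as does ASA IV. A figure of 99% cancer arises only if surgical patients without cancer resemble healthy controls. The only cancer means with SDs come from gastric cancer, whereas the cohort covers all elective major non-cardiac surgery.

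**suPAR may predict beyond stage.** In 518 colorectal cancer patients it remained associated with mortality after adjustment for age, sex, tumour classification and localisation (HR 1.74, 1.33–2.26). This stands, and it makes the no-effect scenario a bounding case, not a forecast. But that study made the adjustment. SPARSE plans none, so it could not show the same thing itself.

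**Prediction does not need causal adjustment.** This is correct for raw discrimination, and enrolling cancer patients in an unselected surgical cohort is a legitimate choice. The objection does not cover a claim that suPAR adds to what is already known before surgery.

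**Reach.** The calculation concerns 1-year survival, a secondary endpoint; no effect on the 60-day composite has been quantified. The odds ratios are crude, and ASA and CRP, if fitted jointly with suPAR (the plan does not say), could absorb some of the effect. Both limits stand.

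**Stratum-by-stratum proof is out of reach.** With the counts in Step 5, requiring the association to hold within each malignancy group could not be tested.

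**Conclusion.** The concern holds as a gap in analysis and interpretation; it does not invalidate the design. The documents establish that cancer of any stage is eligible, that suPAR tracks cancer and stage, that survival runs to 1 year, and that no analysis names malignancy. A crude mortality contrast could therefore partly reflect known diagnosis and stage.

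The size is unknown. The spurious odds ratio stayed above 1 in every scenario tried, from about 1.2 to 5.3, but case mix, non-cancer suPAR and mortality are all assumed. Only the gastric cancer and healthy-control means and SDs, the emergency-patient range and the cut-off come from the plan. Neither a mainly-cancer suPAR-high group nor any single odds ratio should be presented as following from the documents.

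**What to change.** Add to the statistical section, before survival data are analysed:

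1. Derive malignancy status (none, localised, metastatic) for every patient from the ICD-10 diagnoses needed for the Charlson score, checked against the surgical record where coding is incomplete.
2. Report suPAR levels and 90-day and 1-year survival descriptively by cancer status.
3. Give the suPAR estimate for mortality both unadjusted and adjusted for malignancy status. Because deaths will be few, use a single term (for example cancer yes/no, or the three levels scored in order) or a penalised model.
4. State the reading in advance. If the association does not hold after adjustment, or is too imprecise to judge, report only that suPAR is associated with mortality, and make no claim that it adds to known diagnosis and stage. Do not require the association to persist within each stratum.

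The cost is a few sentences and a derived variable from data already planned. The downside is a wider interval and possibly a smaller headline association.

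### The plan cannot show whether suPAR adds prognostic information beyond renal function, although the protocol says renal and hepatic dysfunction affect suPAR

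*Combined protocol and SAP*

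**What the plan says.** Three parts of the document bear on this.

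- **Background, suPAR in intensive care:** "In particular hepatic and renal dysfunction affects the suPAR level". The sentence before it reads "In patients with organ dysfunction, the suPAR value is often a two-digit value", which is well above the study's cut-off.
- **Methods, Patient eligibility:** admits "American Society of Anesthesiologists' (ASA) physical status I to IV". On kidney and liver it excludes "severe liver disease, patients on renal replacement therapy pre-operatively" and "patients who had previously received a transplant". It sets no limit on creatinine, eGFR or stage of chronic kidney disease, and does not define severe liver disease.
- **Sample size and predefined statistical analysis plan:** patients are split at one fixed value ("suPAR_{high} above and suPAR_{low} below 5.5 ng/ml"). The analysis is then given as: "The association between ASA classification, suPAR level, CRP and the rate of postoperative complications will be analyzed with logistic regression and Cox regression analyses". It does not say whether the three variables enter one model together. It names no renal or hepatic term, stratification or sensitivity analysis.

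Data Collection and Monitoring lists P-POSSUM, ACS-NSQIP, APACHE II, SOFA and the Charlson score. Nothing says that any of them will adjust the suPAR association.

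**The concern.** Renal function could plausibly be linked both to the marker, as the protocol says, and to the outcome, which is an assumption here. If so, some of any association between suPAR and the primary endpoint would be information that a routine creatinine already carries. The question matters for this study because the reference cited for the 5.5 ng/ml cut-off presents suPAR, in its title, as adding to established preoperative risk assessment. A positive result from the analysis as planned would leave open whether suPAR tells the clinician anything that renal function does not. CRP is in the planned regressions; renal function is not.

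**Working it through.** The plan gives no figure on this point to reproduce, and no suPAR values or event risks by renal function. The check therefore compares the sections and then sizes the effect under stated assumptions.

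**Step 1: does any section close the gap?** Restriction does not: dialysis, severe liver disease and transplant are excluded, but ASA I to IV leaves room for advanced renal impairment without dialysis. Adjustment does not: only ASA, suPAR and CRP are named. No stratified or sensitivity analysis is planned.

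**Step 2: size.** Split the cohort by renal impairment (yes/no) and let suPAR have no effect within either stratum. Write:

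- q = share with renal impairment
- h1, h0 = share above 5.5 ng/ml with and without it
- e1, e0 = event risk with and without it

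Then:

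- H = q·h1 + (1−q)·h0 (share suPAR-high)
- eH = [q·h1·e1 + (1−q)·h0·e0] / H
- eL = [q·(1−h1)·e1 + (1−q)·(1−h0)·e0] / (1−H)
- crude OR = [eH/(1−eH)] / [eL/(1−eL)]

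All inputs are assumptions:

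- Set A: h1 = 0.40 to 0.60, h0 = 0.10, e1 = 0.50, e0 = 0.25.
- Set B: h1 = 0.50 to 0.80, h0 = 0.20, e1 = 0.40 to 0.50, e0 = 0.25.

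Worked example at the high end (set A, q = 0.20, h1 = 0.60):

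- H = 0.12 + 0.08 = 0.20
- eH = (0.12×0.50 + 0.08×0.25)/0.20 = 0.08/0.20 = 0.40
- eL = (0.08×0.50 + 0.72×0.25)/0.80 = 0.22/0.80 = 0.275
- OR = (0.40/0.60)/(0.275/0.725) = 1.76

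Worked example at low prevalence (set A, q = 0.02, h1 = 0.40):

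- H = 0.008 + 0.098 = 0.106
- eH = (0.004 + 0.0245)/0.106 = 0.269
- eL = (0.006 + 0.2205)/0.894 = 0.253
- OR = 1.08

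| Renal impairment (q) | Crude OR, set A | Crude OR, set B | Renal share of suPAR-high group, A | Same, B |
|---|---|---|---|---|
| 2% | 1.08–1.14 | 1.03–1.10 | 8–11% | 5–8% |
| 5% | 1.19–1.31 | 1.07–1.22 | 17–24% | 12–17% |
| 10% | 1.33–1.52 | 1.12–1.41 | 31–40% | 22–31% |
| 15% | 1.43–1.66 | 1.17–1.55 | 41–51% | 31–41% |
| 20% | 1.50–1.76 | 1.20–1.67 | 50–60% | 38–50% |

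These are crude odds ratios. If ASA is fitted jointly with suPAR, it would take up some of the renal comorbidity and the figures would be smaller.

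**Step 3: what can 100 patients carry?** Under set A at q = 0.10 to 0.20, expected events are 100×(0.10×0.50 + 0.90×0.25) = 27.5 to 100×(0.20×0.50 + 0.80×0.25) = 30. Adding eGFR to suPAR, CRP and four-level ASA makes 1 + 1 + 1 + 3 = 6 parameters, or 4.6 to 5 events each. A model with suPAR and eGFR alone has 13.8 to 15 events per parameter.

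**The case against.** The strongest objection is that this is a prediction study. The aim is to see whether suPAR predicts complications and death, and the background presents it as a non-specific prognostic marker. A patient whose suPAR is high because of renal disease, and who is at higher risk, is classified correctly. This stands. A reader might infer that such patients are wrongly labelled high-risk, and the documents do not support that.

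The background also reports that, in 902 patients with SIRS, suPAR was a stronger marker of mortality than creatinine. That counts against treating suPAR as a mere proxy for creatinine. It does not settle the matter, because those were acutely ill patients and relative strength is not the same as added value.

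The sentence on renal and hepatic dysfunction sits in the intensive-care section, so the effect in elective patients is unknown. The opening background section does, however, also link suPAR to chronic renal and hepatic disease.

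A reader might also infer that the exclusions fail in their purpose. The protocol gives no rationale for any exclusion, and several, such as legal incapacity, need have nothing to do with suPAR. The gap is a limit on what can be concluded, not a contradiction in the eligibility rule.

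Finally, renal function is one candidate among several. The background also ties suPAR to age, cancer and chronic disease generally. Renal and hepatic dysfunction are singled out here because the protocol itself does so.

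**Conclusion.** The point holds as a question of incremental value: the analysis as planned cannot show whether suPAR adds prognostic information beyond renal function. Its size depends on how common renal impairment is among those enrolled, which the documents do not say. The effect is small if it is rare (crude OR about 1.03 to 1.14 at 2%) and material if it is common (about 1.2 to 1.8 at 15% to 20%). Every input to those figures is assumed, including a higher event risk with renal impairment.

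It would be tempting to say that part or all of any suPAR association is really renal. The documents do not support that: the larger odds ratios need a high prevalence of renal impairment of any degree, while advanced impairment without dialysis could be much rarer. This is a cheap improvement to consider, not a flaw that undermines the main analysis.

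**What to change.** Keep enrolment and the main model as they are.

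1. **Data items.** Record preoperative creatinine/eGFR and bilirubin as separate variables. By the scores' standard definitions, creatinine enters both SOFA and APACHE II, and bilirubin enters SOFA. The protocol lists only the scores, without components or timing, so first confirm that preoperative values are available.
2. **Secondary model.** Pre-specify one model for the 60-day primary endpoint that adds continuous eGFR to suPAR, with few other terms given N = 100. Report the suPAR estimate and its interval with and without eGFR.
3. **Sensitivity analysis.** Pre-specify one analysis excluding patients with markedly reduced eGFR or abnormal bilirubin. Fix the analysis thresholds before suPAR results are unblinded.

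The cost is a few lines in the analysis plan and, if the values are not already kept, extra fields on the collection form. The statistical price is one more parameter with few events, a wider interval and possibly a smaller suPAR estimate.
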